5.4. Management of Clinical Supplies

5.4.1. Study Drug Packaging and Storage

Galinpepimut-S will be provided as a sterile, lyophilized powder filled into a 2 mL colorless glass vial that requires reconstitution with SWFI. Galinpepimut-S should be stored at the site at or below -20°C until use.

Montanide will be packaged in 3-mL amber glass vials. The adjuvant should be stored between 15°C and 30°C . This product must not be frozen.

Avoid freezing and thawing of the emulsified product.

Sargramostim (GM-CSF) will be provided in lyophilized form as a 250- μ g sterile, white, preservative-free powder that requires reconstitution with sterile water for injection. It should be stored at 2°C to 8°C. For this study, the vial of GM-CSF is intended for single-use only.

Pembrolizumab will be provided by the sponsor as summarized in Table 7.

Table 7 Pembrolizumab Product Description

Product Name & Potency	Dosage Form
MK-3475 100 mg/ 4 mL	Solution for Injection

These supplies will be shipped by the Sponsor indirectly via their Drug Supply packaging, distribution, and logistics vendor (Sharp Clinical Services, Phoenixville, PA, USA) to investigative sites in the appropriate packaging to maintain their recommended temperatures. The supplies are to be stored in their original cartons at the recommended temperatures until ready for use. Until dispensed to the patients, these supplies will be stored in a securely locked area, accessible to authorized personnel only.

5.4.2. Test Article Accountability

The investigator or designee will maintain accurate records of receipt for all study treatment, including dates and quantities of study drug(s) received. The study treatment will be used in accordance with the protocol by patients who are under the direct supervision of the investigator. The study treatment will be dispensed only by an appropriately qualified person to patients in the study. Accurate records will be kept regarding when, how much, and to whom study treatment is dispensed and administered (patient-by-patient, dose-specific accounting). Reasons for departure from the expected dispensing regimen, including study treatment lost or accidentally or deliberately destroyed, will be recorded. The investigator or designee will retain all used, unused, or expired study supplies until the study monitor has

confirmed the accountability data and the sponsor has approved return or destruction. All clinical study treatments and/or supplies will either be destroyed by the site per institutional policy, or be returned to SELLAS or its designee for destruction per applicable regulations.

5.4.3. Other Supplies

Additional supplies provided for this study will be described in the study pharmacy manual.

5.4.4. Blinding

This is an open-label study.

5.4.5. Breaking the Blind

Not applicable.

5.5. Treatment Compliance

Every effort should be made to follow the administration schedule for galinpepimut-S and pembrolizumab. If a patient misses a scheduled administration of either the combination or pembrolizumab alone, the drug(s) should be administered as soon as possible thereafter. If the patient is more than one-half the time interval to the next scheduled administration, the patient should skip that preplanned administration and have the next administration on schedule. The disposition of study treatment received by the site, dispensed and administered to the patient, returned to the sponsor, destroyed, lost, etc. must be recorded in the site's pharmacy log.

5.6. Prior and Concomitant Therapy

Any treatments or therapies other than the study treatment, including biologics; blood products; prescription drugs; over-the-counter medications; and complementary or alternative medications including herbal products/supplements, vitamins, and minerals that the patient is

receiving will be documented. Use of all concomitant medications will be recorded in the patient's source document and eCRF. Any changes in concomitant medications will also be recorded in the patient's source document and eCRF within 28 days from such a change.

Any concomitant medication deemed necessary for the welfare of the patient during the study may be given at the discretion of the investigator. However, it is the responsibility of the investigator to ensure that details regarding the medication are recorded in full in the eCRF and to consult with the study medical monitor if prohibited medications are considered necessary.

The following medications/treatments are prohibited:

- Other investigational agents given within 4 weeks prior to starting study treatment and during the on-treatment portion of the study.
- Systemic glucocorticoids for any purpose other than to modulate symptoms from an event of clinical interest of suspected immunologic etiology. The use of physiologic doses of corticosteroids is allowed, in dosing that does not exceed a total of 10 mg daily of prednisone (or equivalent). If systemic corticosteroids are required for treatment of a co-morbid illness during the study, the investigator should confer with the medical monitor.
 - Note: Inhaled steroids are allowed for management of asthma.
- Immunosuppressive therapies are prohibited throughout the on-treatment portion of the study.
- Patients must have received their last dose of chemotherapy within 3 months before receiving study treatment. Any concurrent cytotoxic chemotherapy, radiation therapy, hormonal therapy, immunotherapy, biologic therapy, or other systemic therapy for cancer is prohibited during the on-treatment portion of the study.

- Radiation therapy
 - Note: Radiation therapy to a symptomatic solitary lesion or to the brain may be considered on an exceptional case by case basis after consultation with sponsor. The patient must have clear measurable disease outside the radiated field. Administration of palliative radiation therapy will be considered clinical progression for the purposes of determining PFS.
- Live vaccines within 30 days prior to the first dose of trial treatment and while participating in the trial. Examples of live vaccines include, but are not limited to, the following: measles, mumps, rubella, chicken pox, yellow fever, rabies, BCG, and typhoid (oral) vaccine. Seasonal influenza vaccines for injection are generally killed virus vaccines and are allowed. However, intranasal influenza vaccines (e.g. Flu - Mist®) are live attenuated vaccines, and are not allowed.

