- If restaging bone marrow biopsy immediately after the completion of cycle #4 of HMA therapy demonstrates morphological partial response (PR), then such patients become eligible for the study and can initiate investigational therapy (pembrolizumab and galinpepimut-S), as long as the latter commences prior to the initiation of cycle #5 of the HMA.
- Reasonable efforts will be made by the Contracted Research Organization (CRO), Cancer Insight, LLC, at actively enrolling clinical sites to initiate investigational therapy within 14 +/-7 days from the completion of cycle #4 of HMA therapy, to ensure relative homogeneity in the initiation timing relationship between the two

therapeutic modalities, i.e., HMA and investigational therapy.

Furthermore, for clarification purposes, each cycle of therapy in patients in the AML arm will be defined by the frequency of administration of the study investigational agents

(pembrolizumab and galinpepimut- S), i.e., 3 weeks. This clarification is important, because:

- a. patients in the AML arm will continue their HMA therapy throughout the administration of study investigational agents and
- b. the timing of initiation between HMA cycle #5 and that of the first administration of investigational therapies are de-linked.

[figure not shown]
The study design is shown in

Figure 12 and the overall treatment schedule is provided in **Figure 13**.

The study endpoints are defined in **Section 7**.

Figure 12 Study Design

GALINPEPIMUT-S PLUS PEMBROLIZUMAB (MULTIPLE INDICATIONS) – PHASE 1/2 STUDY Open label, non-comparative, multicenter, multi-arm combination trial; N = 90

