 - a. CRC: 2 or 3 lines; b. OvC: 1 or 2 lines; c. SCLC: 1 line; d. TNBC: 1 line; and e. AML: 0 lines (allo-SCT-eligible status or patients with relapsed [2nd line] AML not allowed)
6. Patients should have experienced resolution of toxic effect(s) of the most recent prior chemotherapy to Grade 1 or less (except alopecia). If the patient received major surgery or radiation therapy of > 30 Gy, they must have recovered from the toxicity and/or complications from the intervention.
7. Specifically for patients in the AML arm, the following subject subgroups are eligible:
 - a. Frontline (1st line) patients treated with HMAs since their initial AML diagnosis
 - b. Patients who have required cytoreductive therapy with hydroxyurea or leukapheresis at the time of their initial AML diagnosis, and who subsequently seamlessly transitioned to HMA therapy

- c. Subjects who have experienced induction early failure after initial therapy with 1 - 2 cycles of a standard chemotherapy (“7+3” and similar regimens) and subsequently immediately treated with HMAs as long as such patients have achieved PR as their best observable response after 4 cycles of HMA therapy (per European LeukemiaNet [ELN] criteria).
8. AML patients should continue treatment with HMAs as long as they cannot achieve a response deeper than PR after the completion of administration of 4 cycles of HMAs.
9. If female, patient is eligible to participate if she is not pregnant, not breast-feeding, and at least 1 of the following conditions:
 - a. Not a woman of childbearing potential (WOCBP)
 - b. A WOCBP who agrees to follow contraceptive guidance (agree to use an adequate method of contraception) starting 30 days prior to the administration of the first dose of study therapy and continuing through 4 months after the last study treatment. The effect of galinpepimut-S on the fetus is unknown.
10. Male patients of childbearing potential must agree to use an adequate method of contraception, starting with the first dose of study therapy through 4 months following the last study treatment. It is unknown whether galinpepimut-S affects the sperm, or could be transmitted to the patient’s partner during sexual activity.

Informed Consent

11. Patients (or legally acceptable representative if applicable) should provide written informed consent for the trial.
12. Patients should have measurable/demonstrable active malignant disease per below:

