- c. AML patients are eligible only if they received first line therapy with HMAs (decitabine or azacitidine) for 4 cycles and achieved only PR at the end of cycle 4.
- d. AML patients shall remain on HMA therapy while receiving investigational therapies.

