4.1.2. Exclusion Criteria

Any prospective patient will be excluded from the study if any of the following criteria apply:

Medical Conditions

Pregnancy Exclusion:

1. A WOCBP who has a positive urine pregnancy test (e.g. within 72 hours) prior to treatment. If the urine test is positive or cannot be confirmed as negative, a serum pregnancy test will be required.

Prior/Concomitant Therapy

2. Has disease that is suitable for local therapy administered with curative intent.
3. Has received prior therapy with an anti-PD-1, anti-PD-L1, or anti PD L2 agent or with an agent directed to another stimulatory or co-inhibitory T-cell receptor (e.g., CTLA-4, OX 40, CD137) and was discontinued from that treatment due to a Grade 3 or higher irAE
4. Has received prior systemic anti-cancer therapy including investigational agents within 4 weeks prior to treatment.

Note: Participants must have recovered from all AEs due to previous therapies to \leq Grade 1 or baseline. Participants with \leq Grade 2 neuropathy may be eligible.

Note: If participant received major surgery, they must have recovered adequately from the toxicity and/or complications from the intervention prior to starting study treatment.

5. Has received prior radiotherapy within 2 weeks of start of study treatment. Participants must have recovered from all radiation-related toxicities, not require corticosteroids, and not have had radiation pneumonitis. A 1-week washout is permitted for palliative radiation (\leq 2 weeks of radiotherapy) to non-CNS disease.
6. Has received a live vaccine within 30 days prior to the first dose of study drug. Examples of live vaccines include, but are not limited to, the following: measles, mumps, rubella, varicella/zoster (chicken pox), yellow fever, rabies, Bacillus Calmette–Guérin (BCG), and typhoid vaccine. Seasonal influenza vaccines for injection are generally killed virus vaccines and are allowed; however, intranasal influenza vaccines (e.g., FluMist®) are live attenuated vaccines and are not allowed.

Prior/Concurrent Clinical Study Experience

7. Is currently participating in or has participated in a study of an investigational agent or has used an investigational device within 4 weeks prior to the first dose of study treatment.
8. Has undergone prior allogeneic hematopoietic stem cell transplantation

Diagnostic assessments

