6.1.5. Relapse Visit

In addition to the SOA above, one additional series of assessments will be performed at the time of tumor (or leukemia) relapse. Indeed, to assess PFS, it is important to document disease relapse. At the time of the “relapse visit”, the following assessments will be performed:

- Collect and update concomitant medication information
- Collect and update AEs
- Obtain ECOG performance score
- Obtain vital signs and document weight
- Collect blood samples for the central laboratory
 - Hematology (CBC with differential and platelet count)
 - Serum chemistry
 - Immune/exploratory correlates
- Evaluate clinical endpoints

For AML patients in specific, PB differentials from CBCs collected during every visit will be used to determine initially if the patient has relapsed, as defined by loss of CR status (if previously achieved) or further progression beyond initially achieved PR. For abnormal CBCs, a manual differential is required. If the differential is suggestive of abnormal or

immature cells and a possible relapse, a BM aspiration must be performed as part of a scheduled relapse visit to confirm the diagnosis of recurrent/relapse/refractory AML. A BM biopsy must be performed if an adequate aspiration is not attainable. In patients with AML who achieve CR status while on investigational therapy (galinpepimut-S plus pemrolizumab – administered on top of their continuing HMA regimen), relapse (post-CR) will be defined as a reappearance of leukemic blasts in the PB or >5% blasts in the BM not attributable to any other cause (e.g., BM regeneration after chemotherapy [[Cheson et al, 2003](#)]). If relapse is confirmed, the patient should be discontinued from the on-treatment portion of the study due to recurrent/refractory/relapsed AML and will need to return to the site 0 to 30 days after their last treatment injection for final safety follow-up and completion of the EOT/early termination visit procedures. The BM aspiration performed as part of the scheduled relapse visit will serve as BM aspiration procedure required at the EOT/early termination visit.

Once EOT/early termination visit procedures have been completed, the physician can choose to treat the documented recurrent/refractory/relapsed disease with any subsequent therapy they choose. The patient will be moved to the off- treatment follow-up period and will be followed only for AEs and OS.

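### Section 5.6 prohibits the hypomethylating agent that every AML patient must keep taking, and exclusion 4 has the same missing exception

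*Combined protocol and SAP*

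**What the plan says.** **Prohibition.** Section 5.6 lists what patients may not receive. One item covers concurrent chemotherapy, radiation, hormonal, immune and biologic treatment, and ends "or other systemic therapy for cancer is prohibited during the on-treatment portion of the study". The section does write exceptions elsewhere, for physiologic-dose steroids, for inhaled steroids ("Note: Inhaled steroids are allowed for management of asthma") and for radiation to certain lesions after discussion with the sponsor. It has none for HMA. For prohibited drugs in general, the investigator is to "consult with the study medical monitor if prohibited medications are considered necessary".

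**Requirement.** The AML arm is built on continued HMA:

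- Section 3.1.1: "patients in the AML arm will continue their HMA therapy throughout the administration of study investigational agents".
- Section 4.1.1, inclusion 8: "AML patients should continue treatment with HMAs as long as they cannot achieve a response deeper than PR".
- Section 4.1.1, AML criterion d: "AML patients shall remain on HMA therapy while receiving investigational therapies".
- Section 6.1.5 describes study therapy in AML as "administered on top of their continuing HMA regimen".

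**Washout.** Exclusion 4 in Section 4.1.2 applies to a patient who "Has received prior systemic anti-cancer therapy including investigational agents within 4 weeks prior to treatment". Its two notes deal with recovery from earlier toxicity and from surgery. Section 3.1.1 requires AML patients to begin study therapy after HMA cycle 4 and before cycle 5, with a target of 14 ± 7 days from completion of cycle 4.

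**The concern.** Two operative rules in the same protocol cannot both be followed. A site that obeys Section 5.6 must stop HMA; a site that obeys AML criterion d must give a prohibited drug. No sentence says which rule takes precedence.

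Three other sections give the conflict practical weight. Section 4.1 allows no deviations from the eligibility criteria. Section 4.2.1 lists the need for a medication prohibited by the exclusion criteria or by Section 5.6 among the reasons a patient may be taken off treatment. Section 1.3.1.2.5 advises against interrupting HMA once a response, including PR, has been reached, and every AML entrant is in PR. Literal compliance, by stopping HMA or by delaying cycle 5 to meet the washout, would go against the protocol's own clinical advice. Non-compliance invites a deviation query for each AML patient.

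**Working it through.** The plan states no figure on this point, so there is none to reproduce. The check sets the texts side by side and then counts days.

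**Step 1: is HMA covered by the Section 5.6 prohibition?** Azacitidine and decitabine given for AML are systemic cancer therapy. Section 5.2 and Table 3 list only galinpepimut-S, Montanide, GM-CSF and pembrolizumab as study products, and Section 3.1.1 treats HMA and investigational therapy as two separate modalities. HMA is therefore concurrent systemic therapy under Section 5.6. All 15 planned AML patients are affected once HMA is given during study therapy.

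**Step 2: can an AML patient meet exclusion 4?** Inputs:

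- Washout required: 4 weeks = 28 days (exclusion 4).
- Latest start of study therapy: before HMA cycle 5 (Section 3.1.1).
- HMA cycle length L: at least 4 weeks (synopsis, Dose-limiting Toxicities). The azacitidine nadir rule gives the next course 28 days after the start of the previous one (Section 5.3.9.1).
- Day of the last HMA dose in cycle 4, D: not stated for the planned regimen, so taken as any D ≥ 1.

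Let cycle 4 start on day 1 and cycle 5 on day L + 1. Study therapy starts by day L at the latest, so

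longest possible gap = L − D, and exclusion 4 needs L − D ≥ 28, that is L ≥ 28 + D.

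| Cycle length L | D = 1 | D = 3 | D = 5 | D = 7 | D = 10 |
|---|---|---|---|---|---|
| 28 days | 27 | 25 | 23 | 21 | 18 |
| 35 days | 34 | 32 | 30 | 28 | 25 |
| 42 days | 41 | 39 | 37 | 35 | 32 |

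At L = 28 the gap is 28 − D ≤ 27 for every D ≥ 1, so the criterion fails whatever the dosing schedule. At L = 42 it can be met for D ≤ 42 − 28 = 14. The reduced decitabine schedule in Section 5.3.9.2 has 99/33 = 3 dosing days per cycle; if these are days 1 to 3, a 42-day cycle gives a gap of up to 39 days.

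**Step 3: does the 14 ± 7 day target change this?** It depends on what completion of cycle 4 means, which the protocol does not define.

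- If it means the last dose, the gap is 7 to 21 days and exclusion 4 fails.
- If it means day 28 of the cycle, study therapy starts on days 35 to 49. The gap is 28 to 42 days at D = 7 and 32 to 46 days at D = 3, which passes. Because study therapy must still precede cycle 5, cycle 5 then starts later than day 29, so the HMA is no longer on a 28-day schedule.

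**Step 4: is an AML exception written anywhere else?** Exclusion 10 has one for prior myelodysplastic or myeloproliferative disease. The AML-specific exclusions in Section 4.1.2.1 have one for patients switched to HMA after one or two induction cycles, but it qualifies the exclusion of relapsed disease. Neither waives the 4-week washout.

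**Step 5: does the AML decision rule change?** No. With n = 15, Go at ≥ 4 and Stop at ≤ 1 responses, the binomial probabilities at true rates of 25/20/15% are Go 53.9/35.2/17.7% and Stop 8.0/16.7/31.9%. These match Table 13 (54/35/18 and 8/17/32) and do not depend on the wording at issue.

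**The case against.** The strongest reply is that the specific text governs the general. HMA continuation appears in the synopsis, the design section, two inclusion criteria and the relapse section, and Section 5.3.9 gives dose-modification rules for both drugs. Only one workable reading exists, and sites will find it. Removal under Section 4.2.1 is optional, Section 5.6 allows medication needed for the patient's welfare, and no endpoint or primary analysis is affected. This largely stands, and it limits the seriousness. It does not remove the contradiction: the protocol states no order of precedence, and case-by-case consultation with the medical monitor is not an exception for a mandatory drug.

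On exclusion 4, the reply is that HMA is ongoing and so not prior therapy, which fits inclusion 5 counting zero lines for AML; and that if completion means the end of the cycle, the protocol's own target window can satisfy the washout. Both readings are possible. The first is nowhere stated, and AML criterion c speaks of first-line HMA as already received. The second works only by moving cycle 5 later, so it does not rescue the on-schedule patient. Exclusion 4 is therefore a conditional problem, whereas Section 5.6 is an unconditional one.

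An effect on the per-protocol set is possible if HMA use were classed as a major deviation. Section 7.5 leaves the detailed definition to the SAP, so no weight is placed on it here.

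**Conclusion.** The concern holds, as a drafting contradiction and not a design error. Section 5.6 as written prohibits required treatment in all 15 planned AML patients. Exclusion 4, read literally, excludes AML patients who start before cycle 5 on an on-schedule 28-day HMA cycle: at most 27 days against the 28 required, with no assumption about the number of dosing days. It can be met once the cycle is at least 28 days plus the day of the last dose. The exclusion 4 part rests on counting ongoing HMA as prior therapy, which the text neither states nor rules out. The FAS-based AML analysis and its boundaries are unaffected. It should be corrected, because eligibility and prohibited-medication rules are applied literally in monitoring.

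**What to change.** In the next amendment, add the words *except protocol-required azacitidine or decitabine in the AML arm* in two places: the concurrent-therapy item in Section 5.6 and exclusion 4 in Section 4.1.2. Section 4.2.1 refers to both, so it needs no separate edit.

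The cost is two short wording changes. Sample size, visit schedule and decision boundaries stay as they are.
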